5 INTRODUCTION

Long-chain fatty acid oxidation disorders (LC-FAOD) are caused by enzyme deficiencies in the metabolic pathway that converts fatty acid into energy, leading to inadequate energy metabolism. LC-FAOD can result in serious and potentially life-threatening clinical manifestations, including rhabdomyolysis, hypotonia/weakness, hypoglycemia, and cardiomyopathy. The clinical manifestations are usually managed through the avoidance of fasting, a low-fat/high-carbohydrate diet, supplementation with medium chain triglycerides (MCT oil) and/or carnitine supplementation. Despite treatment, many patients still suffer significant morbidity and mortality. The mortality rate can be above 50% for subjects diagnosed symptomatically and treated with the standard of care (Baruteau et al. 2012).

Triheptanoin (UX007), a highly purified medium-odd-chain triglyceride consisting of 3 fatty acids with 7 carbons each, is intended as a substrate replacement therapy in patients with LC-FAOD and potentially other metabolic disorders to restore deficient intermediates in the mitochondria required for energy metabolism. Triheptanoin has been studied in many types of LC-FAOD and various other disorders. Some patients have been treated with triheptanoin for approximately 20 years with evidence of clinical benefit and no significant safety issues reported. Published reports suggest that LC-FAOD patients failing current therapy can exhibit profound positive clinical responses to triheptanoin (Roe et al. 2002); (Barone 2012); ([name] et al. 2015); ([name] et al. 2016); ([name] et al. 2017); ([name] et al. 2018).

A retrospective medical record review study (UX007-CL001) has been conducted to formally assess the clinical outcome of triheptanoin treatment in 20 of 24 LC-FAOD patients who have been participating in an ongoing compassionate use program (IND-106011) for up to 13 years. The data suggest triheptanoin is effective in reducing serious and potentially life-threatening energy crises as indicated by a 69% decrease in the number of hospitalization days during major medical events ([name] et al. 2015). The results imply the possibility to reduce major medical events, and provide the basis for further evaluation of UX007 in prospective clinical studies to verify this effect on the clinical manifestations and major events of LC-FAOD disease.

A completed Phase 2 clinical trial (UX007-CL201) evaluated the safety and effectiveness of UX007 in LC-FAOD patients who continued to suffer the effects of LC-FAOD disease despite current therapy. Following completion of a 24-week Treatment Period and 54-week Extension Period, subjects from UX007-CL201 were eligible to continue treatment in this extension study (UX007-CL202). Numerous LC-FAOD patients have also participated, or are actively participating in multiple clinical studies or compassionate use treatment programs with UX007/triheptanoin conducted by various sponsors and investigational sites. This open-label long-term safety extension study will provide an opportunity for these patients and treatment-naïve patients (i.e., naïve to both UX007 and food-grade triheptanoin) with clear unmet need to be treated with UX007 for up to 7 years or until commercial availability of UX007 in any region, whichever occurs first, under a single standardized protocol. The study is designed to obtain long-term safety information and evaluate maintenance of efficacy in a diverse LC-FAOD population.

5.1 Overview of Long-chain Fatty Acid Oxidation Disorders

Inherited autosomal recessive defects in the mitochondrial long-chain fatty acid oxidation pathways are collectively referred to as LC-FAOD. LC-FAOD are caused by defects in the mitochondrial β -oxidation pathways that convert fatty acids into energy, leading to deficiencies in energy metabolism. As a result, partial or incomplete oxidation of fatty acids leads to accumulation of high concentrations of fatty acids or other metabolic intermediates and an energy deficient state in most organs. The clinical manifestations of the various LC-FAOD frequently overlap and include rhabdomyolysis, hypoglycemia, hepatomegaly, cardiomyopathy, hypotonia and developmental delay, as well as sudden infant death (reviewed in Roe et al. 2002).

Clinical surveys suggest patients with LC-FAOD as a group have an overall premature mortality rate from birth of about 50% or higher when diagnosed symptomatically and treated (Baruteau et al. 2012). Mortality may now have been reduced by newborn screening and early presymptomatic treatment, including diligent prevention of fasting combined with the use of low fat/high carbohydrate diets, carnitine supplementation in some cases, and MCT oil supplementation (Spiekerkoetter et al. 2009). MCT oil has medium even-chain fatty acids that can be metabolized by the separate set of medium-chain fatty acid oxidation enzymes that are distinct from those affected in LC-FAOD and should therefore bypass the LC-FAOD block.

Despite improved mortality rates achieved with newborn screening, Spiekerkoetter and colleagues noted that patients on the best available treatment, including MCT oil with compliance of \geq 80%, still had significant problems (Spiekerkoetter et al. 2009). Lindner and colleagues studied the outcome of expanded newborn screening on major decompensation events in different classes of disease diagnosed in South-West Germany (Lindner et al. 2011). The 16 patients (6 very long chain acyl-CoA dehydrogenase [VLCAD], 5 L-3-hydroxy-Acyl-CoA dehydrogenase [LCHAD], 2 carnitine-acylcarnitine translocase [CACT] deficiency, 3 multiple acyl-CoA dehydrogenase [MADD]) in the group had a 25% rate of major decompensation after only 2 years of follow-up.

5.2 Brief Overview of UX007 (Triheptanoin) Development

A brief overview of existing information on UX007 (triheptanoin) is provided below; a comprehensive review of the data is contained in the Investigator's Brochure (IB) provided by Ultragenyx Pharmaceutical Inc. (Ultragenyx), which should be reviewed prior to initiating the study.

[figure not shown]

5.2.1 Brief Description of the Investigational Product

UX007 is a liquid, intended for oral (PO) administration. UX007 is highly purified triheptanoin, a triglyceride of 3 fatty acids with 7 carbons each. UX007 is manufactured by chemical synthesis from glycerol and heptanoic acid. The molecular formula and structure are as follows:

Molecular Formula: C24H44O6

Structure:

Triheptanoin is metabolized to heptanoate, which in turn is further metabolized to 4- and 5- carbon ketone bodies and the 3-carbon propionyl CoA (derived from the 5-carbon ketones). Therefore, UX007 is designed as a pro-drug that is metabolized to heptanoate to provide substrate replacement as an odd-carbon medium-chain fatty acid for both fatty acid metabolism and anaplerosis (replacement of tricarboxylic acid [TCA] cycle intermediates) required for generation of energy.

5.2.1.1 Mechanism of Action

The mechanism of action of UX007 in restoring energy metabolism is dependent on its medium chain length as well as its odd-carbon properties. UX007 can be metabolized by LC-FAOD patients into free heptanoate which can traverse the mitochondrial membrane without the carnitine carrier. The free heptanoate from UX007 is then metabolized by a different set of medium chain fatty acid oxidation enzymes, bypassing the long chain oxidation enzymes that are deficient in LC-FAOD. The heptanoate is converted to both propionyl-CoA and acetyl-CoA required for energy metabolism (Figure 5.2.1.1.1). The restoration of energy metabolism is accomplished by two modalities: 1) the acetyl-CoA is condensed into citrate, the first step of the energy generating TCA cycle, and 2) the 3-carbon unit in propionyl-CoA resupplies the TCA cycle intermediates that may be secondarily deficient in these patients. The production of propionyl-CoA is specific to odd-carbon fatty acids and is responsible for the anaplerotic properties of UX007, which are believed to be critical for restoring the energy deficiency state in LC-FAOD.

[figure not shown]
[figure not shown]

Figure 5.2.1.1.1: Mechanism of Action

Propionyl-CoA is a particularly efficient compound for restoring depleted TCA cycle intermediates due to the low succinyl-CoA concentration which can differ by 2-3 orders of magnitude compared to other compounds in TCA cycle intermediate pools. Propionyl-CoA is an anaplerotic substrate for all tissues, and is also gluconeogenic in the liver, kidney cortex, and brain (Kinman et al. 2006); (Gu et al. 2010); (Marin-Valencia et al. 2013). Production of anaplerotic propionyl-CoA stimulates acetyl-CoA oxidation, NADH production, and ATP regeneration, which should result in improved cardiac and skeletal muscle function. Although it is clear that even-carbon medium-chain triglycerides such as MCT oil can help LC-FAOD patients by bypassing defects, the additional effect of anaplerosis, and subsequent gluconeogenesis, is believed to be responsible for the further benefits observed in triheptanoin clinical programs.

In addition to restoration of energy metabolism, UX007 reduces the production of toxic fatty acid intermediates by providing an external source of energy which is preferentially utilized over endogenous long-chain fatty acids, thus suppressing lipolysis. UX007 provides an efficient source of energy from fatty acids for muscles, potentially preserving glucose and glycogen stores during periods of fasting. This leads to a potentially more stable energy state whereby fasting and exercise episodes can be better tolerated due to both increased energy stores and also leads to better utilization of fats and ketone bodies as energy sources.

5.2.2 Nonclinical Studies

Studies of potential clinical significance and relevance to this protocol are summarized below. Additional details are provided in the UX007 IB.

Nonclinical studies evaluating triheptanoin and its metabolites in mice and rats have been published and further support the safety of UX007. These studies provide data on the absorption, and metabolism of triheptanoin when administered intravenously and PO at doses up to 40% the recommended caloric intake. Triheptanoin is metabolized rapidly in the gut to form a series of energy containing metabolites, including heptanoate, C4- and C5-ketone bodies (Kinman et al. 2006), (Deng et al. 2009).

Nonclinical studies in rats have demonstrated that triheptanoin is hydrolyzed to heptanoate and glycerol, which are efficiently absorbed by the liver (Kinman et al. 2006). A study in mice infused with intravenous ¹³C-heptanoate at 50% the caloric requirement demonstrated increased plasma ¹³C-enriched glucose levels over baseline plasma glucose levels, confirming that heptanoate is a substrate for gluconeogenesis in the liver (Marin-Valencia et al. 2013). Gu et al. also showed that triheptanoin infusion can generate glucose and also increase glycogen stores in liver (Gu et al. 2010).

The acute oral toxicity of triheptanoin was performed in rats at four dose levels ranging from 0.5 ml/kg (n= 2) to 5 ml/kg (n=5M/5F). There were no deaths or signs of toxicity at any time throughout the duration of the study and up to 7 days post dose (IND-59303).

A 9 month oral toxicity study in rats was performed with an experimental oil containing 64% triheptanoin to determine the effects of a diet containing triheptanoin on animal growth, lipid digestibility, clinical chemistry, and toxicity in liver, kidney, and small intestine (Ataide et al. 2009). After 9 months of consumption of a standard diet containing doses up to 1.14 g triheptanoin per kg of body weight per day, no toxic effects attributed to triheptanoin were found in rats. There was no significant difference in the clinical chemistries that would indicate hepatic damage or adverse effect on renal function compared to control animals fed a standard diet supplemented with soybean oil as the lipid source.

A Good Laboratory Practice (GLP) 9-month chronic toxicology study in juvenile Yucatan Mini-Pigs has been completed. UX007 was well tolerated for 9-months with no evidence of toxicity in mini-pigs receiving up to 50% of their daily caloric intake from UX007. Systemic exposure to UX007 was evident from the dose-related increase in its primary metabolites (heptanoic acid and C5 ketone bodies). No accumulation was seen after 9 months of treatment. No gross or microscopic lesions were noted due to UX007 administration at any of the dose levels. Based on the lack of toxicity in these animals after 9 months of treatment, the no observed adverse effect level (NOAEL) for systemic toxicity following oral administration of UX007 to juvenile Yucatan minipigs was 50% of daily caloric intake.

5.2.3 Previous Clinical Studies

Over 500 subjects with various diseases have been treated with triheptanoin for up to approximately 20 years. The clinical experience supports the safety of triheptanoin when administered at approximately 35% of daily caloric intake in pediatric patients as young as neonates.

Triheptanoin has been studied for over a decade in a large cohort of LC-FAOD patients (Roe et al. 2002), (Roe et al. 2006), (Roe et al. 2008), (Barone 2012). Patients with other disorders have also been treated with triheptanoin, including those with pyruvate carboxylase deficiency (Mochel et al. 2005), Huntington's disease (Mochel et al. 2010), adult polyglucosan body disease (APBD, a form of glycogen storage disorder due to brancher enzyme deficiency; (Roe et al. 2010), and Pompe disease (also known as glycogen storage disease type II [GSD-II] or acid maltase deficiency; (Roe et al. 2006). Ultragenyx also evaluated UX007 as treatment for Glut1 deficiency syndrome (Glut1 DS). The use of UX007 in the Glut1 DS indication is no longer under clinical development as the clinical studies did not meet their primary efficacy endpoints.

Roe and colleagues described triheptanoin treatment of 3 subjects with VLCAD (Roe et al. 2002). Despite 2 - 5 years on standard of care including MCT oil as fat supplement, all subjects had numerous clinical problems. Within hours of initiating triheptanoin treatment, improvements in muscle pain and function were seen in all subjects. Within 1 week, both subjects with hepatomegaly had normal liver size. The subject with cardiomyopathy had a shortening fraction (SF) of 19% prior to treatment which improved to 30% after 1 month on triheptanoin therapy.

A cumulative summary of triheptanoin treatment was reported for 48 LC-FAOD patients by Roe and Mochel (Roe et al. 2006). Following initiation of triheptanoin, a large decrease in hepatomegaly/hypoglycemia in nearly all patients was observed. Substantial decreases in rhabdomyolysis event frequency, and a decrease in cardiac disease were also reported.

Roe and colleagues described the impact of triheptanoin treatment in 7 patients with carnitine palmitoyltransferase type II (CPT II) deficiency (Roe et al. 2008). During the 18 month assessment period, there were no rhabdomyolysis events or hospitalizations, and all patients returned to normal physical activity within 2 months following initiation of triheptanoin. The treatment was well tolerated when triheptanoin was consumed over a 20-30 minute period (Roe et al. 2008).

In total, 61 LC-FAOD patients have been treated with triheptanoin by [name] and colleagues in a study sponsored by the Baylor Research Institute (IND-59303). A subset of subjects continued triheptanoin treatment for up to 10 years as part of a compassionate use program. These patients were transferred to the University of Pittsburgh Medical Center, under [name] and their treatment continued (IND-106011). Some of these patients have been reported to exhibit profound clinical responses to triheptanoin including reduction of frequency and severity of rhabdomyolysis events, reduction or elimination of

hypoglycemia events, improved physical capacity, and resolution of cardiomyopathy (Roe et al. 2002); (Barone 2012). Anecdotal evidence suggests triheptanoin treatment is well tolerated and does not result in excess weight gain with proper management of caloric intake (Barone 2012).

A retrospective medical record review study (UX007-CL001) was conducted for LC-FAOD subjects who have been treated with triheptanoin for 0.6 - 13 years under the aforementioned treatment program ([name] et al. 2013). The study evaluated the impact of triheptanoin treatment on the rate and extent of hospitalizations in 20 of 24 patients who consented to be part of the study. A total of 120 individual charts were evaluated, which covered 241 years of patient data and included a total of 319 hospitalizations. The study compared the major medical event rate before and after initiation of triheptanoin treatment including the total number of hospitalizations and hospital days per year due to all causes, muscle rupture, hypoglycemia, or cardiomyopathy. Results demonstrated significant decreases in the number of hospitalization days during major medical events (69%; p < 0.05), and the mean number of hypoglycemia events per year (96%; p<0.01) after initiation of triheptanoin treatment ([name] et al. 2015).

In the Phase 2 study, UX007-CL201, the frequency and duration of major clinical events including rhabdomyolysis, hypoglycemia, and cardiomyopathy were consistently reduced during 78 weeks of UX007 treatment compared with the 78-week pre-UX007 period ([name] et al. 2018), supported by the consistent results from the retrospective study CL001. In addition to total events, a clinically meaningful reduction in events leading to hospitalizations was observed, indicating an effect of UX007 on the most serious manifestations of LC-FAOD. Walking distance improved for the 12 Minute Walk Test (12MWT) in UX007-CL201, indicating that subjects maintained pace and exhibited increased stamina throughout the entire distance walked, consistent with an improvement in energy metabolism. In addition, both workload and duration improved during cycle ergometry testing following 24 weeks of UX007 treatment, with an observed 60% mean increase in workload over Baseline, suggesting the potential for improved exercise capacity following treatment with triheptanoin ([name] et al. 2017).

5.3 Summary of Overall Risks and Potential Benefits

UX007 is intended as a substrate replacement therapy to restore the full process of energy metabolism in patients with LC-FAOD. Triheptanoin was developed to address the needs of LC-FAOD patients who continued to have disease crises despite the best available treatment. The current standard of care for these patients is not sufficient to prevent all LC-FAOD manifestations, and is still associated with a high mortality rate (Baruteau et al. 2012).

Over 500patients with various disorders, including LC-FAOD patients ranging from neonates to adults, have been treated with triheptanoin for up to approximately 20 years with evidence of clinical benefit and no significant safety issues reported. Published reports indicate that triheptanoin has improved a wide range of LC-FAOD symptoms in the subjects studied and some LC-FAOD patients failing current therapy can exhibit profound positive clinical

responses to triheptanoin, including a reduction of frequency and severity of rhabdomyolysis events, reduction or elimination of hypoglycemia events, improvements in liver function and hepatomegaly, improved physical capacity, and resolution of cardiomyopathy.

Nonclinical studies evaluating triheptanoin and its metabolites in mice and rats have been published and further support the safety of triheptanoin in the LC-FAOD population. Data from pharmacokinetic and toxicity studies indicates that triheptanoin is well absorbed after oral dosing and is well-tolerated without overt toxicities at doses as high as 1.14 g/kg for 9 months. There were no signs of hepatic or renal injury.

Data from nonclinical and clinical studies to date suggest triheptanoin does not pose any significant safety risks that can be identified at this time. Triheptanoin has been well tolerated in humans with no significant safety issues and toxicology or adverse pharmacology findings were not observed in triheptanoin-treated animals. Studies in animals and humans suggest triheptanoin consumed orally has side effects that are similar to those of orally consumed medium chain triglycerides.

In clinical trials with UX007, the most common treatment-related treatment-emergent adverse events (TEAEs) were gastrointestinal (GI) in nature. Of these most frequently reported TEAEs were diarrhea and abdominal pain, which were mild or moderate in severity, and mostly occurred during up-titration of the initial dose of triheptanoin, and lasted a median duration of 3 days. Where it was deemed clinically necessary in the judgment of the Investigator, treatment-related GI events may be managed with UX007 dose reductions. The adverse drug reactions for triheptanoin in subjects with LC-FAOD are diarrhea, abdominal pain (including preferred terms of abdominal pain, abdominal pain upper, abdominal discomfort, abdominal distention, and gastrointestinal pain), vomiting and nausea.

Overall the risk-benefit ratio of triheptanoin/UX007 appears to be favorable based on the safety record to date and the benefit observed in published observational studies, compassionate use programs, and Ultragenyx clinical trials.

5.4 Study Rationale

LC-FAOD are caused by defects in the metabolic pathway that converts fatty acids into energy, leading to deficiencies in energy metabolism. The metabolic deficiency can deplete energy sources, resulting in serious clinical manifestations including hypotonia, rhabdomyolysis, liver dysfunction and hypoglycemia, and cardiomyopathy. These LC-FAOD major events are not sufficiently controlled in many patients by current standard of care, usually consisting of avoidance of fasting, low-fat/high-carbohydrate diet, dietary medium chain triglycerides (MCT oil), and/or carnitine supplementation. MCT oil, an even chain fatty acid, can provide medium chain fatty acids that bypass the specific LC-FAOD pathway defects but may not restore energy metabolism fully. In addition to supplying medium chain fatty acids, UX007 (triheptanoin), a specialized medium odd-chain (C7) triglyceride, also replaces deficient mitochondrial TCA cycle intermediates via the generation of 3-carbon intermediates, thereby improving energy metabolism.

At the time of protocol development, triheptanoin had been studied in many types of LC-FAOD for more than 13 years. Published reports describe profound clinical responses to triheptanoin, including improved physical capacity and a reduction of frequency and severity of major LC-FAOD events (rhabdomyolysis, hypoglycemia, liver function and hepatomegaly, and cardiomyopathy). Numerous LC-FAOD patients have participated, or are actively participating in multiple clinical studies or treatment programs with UX007/triheptanoin conducted by various sponsors and investigational sites.

This open-label long-term safety and efficacy extension study will provide an opportunity for LC-FAOD patients to be treated with UX007 for up to 7 years or until commercial availability of UX007 in any region, whichever occurs first, under a single standardized protocol. The subjects may have participated in other studies or treatment programs with UX007/triheptanoin or be treatment naïve and have clear unmet need but would be consolidated into one program for long-term maintenance and consistent safety monitoring. The study is designed to obtain long-term safety and efficacy information and evaluate maintenance of efficacy in a diverse LC-FAOD population.

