7.2 Discussion of Study Design, Including Choice of Control Group

The primary objective of this open-label Phase 2 extension study is to evaluate the long-term safety and efficacy of UX007 in patients with LC-FAOD. The study will also explore long-term effects of UX007 on energy metabolism and clinical events associated with LC-FAOD. Evaluations of biomarkers will also be performed to provide supportive evidence and potentially confirm surrogate endpoints of efficacy. LC-FAOD laboratory measures may potentially provide supportive evidence of effects on energy metabolism and safety.

The sample size is intended to provide the maximum amount of information regarding UX007 long-term safety and efficacy in a diverse LC-FAOD population. Since all subjects will receive the same investigational product, randomization and blinding are unnecessary; study drug will be provided open-label.

Any historical data obtained from medical records will be used as a comparator for the Treatment Extension Period, enabling those subjects to represent an internal control for assessment of efficacy. While the lack of a parallel control group may introduce difficulties in discerning natural disease progression from treatment effectiveness, a placebo -controlled study of this duration is difficult to conduct and possibly not ethical given the need for ongoing disease management, and the potential for acute, life-threatening crises in untreated patients.

Given the acute-on-chronic nature of LC-FAOD, subjects will be eligible to continue maintenance UX007 treatment for up to 7 years (84 months) or until commercial availability of UX007 in any region, whichever occurs first. The treatment duration is intended to provide additional long-term safety information and provide sufficient insight on sustained clinical effects in LC-FAOD patients under a single study protocol.

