8.5.5.1 Pre- and Post-UX007 MCEs in CL201-Rollover Cohort

Annualized event and duration rates of MCE and by MCE type will be calculated for the three time periods: study period 3 (i.e., 18 months pre-UX007 treatment period), the 18 month CL201 treatment period, and study period 1 (CL202 UX007 treatment period). Within study period 1, annualized event/duration rates will be calculated by 18-month time interval. Summary statistics will be provided for calculated annualized event/duration rates. In addition, annualized event/duration rates will be plotted as box plots over time to show the time trend.

Annualized event rates (AER) and Annualized Event Duration rates (AED) will be analyzed by comparing pre- and post-UX007 treatment period. The pre-UX007 treatment period for UX007-CL201 Rollover subjects corresponds to study period 3.

For subjects who had longer than 18 months of follow up on study (CL202) as of the data cutoff date, MCEs that occurred between UX007 initiation and 18 months post UX007 initiation will be included for calculating number of MCEs and total durations in days of MCEs will be calculated accordingly. For subjects who terminated the study prior to reaching 18 months on study, MCEs that occurred between UX007 initiation and the termination visit will be included for calculating number of MCEs and total durations in days of MCEs will be calculated accordingly. For historical annualized event rate and annualized duration rate observed during study period 3, the data collection period is 18 months (548 days) preceding the date of UX007 initiation. For subject's age less than 18 months at UX007 initiation, the data collection period will be between the birthdate and the date prior to UX007 initiation.

Patient level plots to show all MCEs over time and time-points of start of retrospective period relative to the UX007 initiation and early discontinuation in a subject if applicable will be presented.

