8.5.5.2 Sensitivity Analyses for CL201-Rollover Cohort

8.5.5.2.1 Negative Binomial Regression in CL201-Rollover Cohort

The comparison between pre- and post-UX007 MCE rates will also be performed using a negative binomial regression model, which accounts for different follow-up times, with the time that each subject stays in the study included as an offset in the model. This analytic model estimates the ratio of event rate of the post-UX007 treatment period over that of the pre-UX007 treatment period. The model can be performed using SAS GENMOD procedure where the REPEATED statement is used to account for the within patient comparison. Two-sided 95% confidence interval will be provided for the rate ratio along with the p-value.

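### In CL201 rollovers, maintenance of efficacy is assessed only descriptively: no within-subject CL202:CL201 rate ratio or interval is planned, and the pre/post comparison is nearly insensitive to waning in CL202

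*Protocol*

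**What the plan says.** The aim in Protocol 5.4 is "The study is designed to obtain long-term safety and efficacy information and evaluate maintenance of efficacy in a diverse LC-FAOD population". Protocol 7.2 adds that the treatment duration should "provide sufficient insight on sustained clinical effects in LC-FAOD patients under a single study protocol".

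For CL201 rollovers, SAP 8.5.5.1 calculates MCE event and duration rates separately for study period 3 (before UX007), the CL201 treatment period and study period 1 (CL202). It goes further within CL202: "Within study period 1, annualized event/duration rates will be calculated by 18-month time interval". The outputs are summary statistics, patient-level plots of all MCEs, and a group display in which "annualized event/duration rates will be plotted as box plots over time to show the time trend".

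The between-period comparison is of another kind: "Annualized event rates (AER) and Annualized Event Duration rates (AED) will be analyzed by comparing pre- and post-UX007 treatment period". For subjects with more than 18 months on CL202, "MCEs that occurred between UX007 initiation and 18 months post UX007 initiation will be included for calculating number of MCEs". The section names no test. SAP 8.5.5.2.1 adds a negative binomial model: "This analytic model estimates the ratio of event rate of the post-UX007 treatment period over that of the pre-UX007 treatment period". It reports that ratio with a 95% confidence interval and a p-value.

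Table 11.1.1 describes the rollover MCE analysis differently, as periods 2 and 3 with descriptive statistics only.

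**The concern.** In an extension study, the natural question about maintenance is whether the event rate in the extension holds at the level reached in the parent study. Rollovers can answer it within subject, because each contributes CL201 and CL202 time. Yet the only contrast that carries an interval and a p-value is post against pre. That asks whether treatment was better than no treatment, a question CL201 already addressed.

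Two things are at stake. First, the pre/post ratio could be cited as long-term evidence although, on the most natural reading of the SAP, it contains almost no CL202 time. Second, marginal summaries and box plots of skewed, low-count rates do not use the pairing of periods within subjects. They give no uncertainty for the change, so a reader could neither support a claim of maintenance nor separate waning from noise. Partial waning is the harder case. With assumed rates of 1.5 before treatment, 0.75 in CL201 and 1.2 in CL202, (1.2 − 0.75)/(1.5 − 0.75) = 60% of the benefit is lost, yet CL202:pre is 1.2/1.5 = 0.8 and still looks favourable.

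**Working it through.** The documents give no event rate, rollover number, dispersion or maintenance margin, so there is no planned figure to reproduce. The time windows can be checked exactly. The rest is illustration on stated assumptions.

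**1. What the 18-month post window contains**
- For rollovers, UX007 treatment day 1 is the first dose in CL201 (SAP 5.4).
- Study period 3 is the 548 days before that day (SAP 5.10.3). Check: 1.5 × 365.25 = 547.9, which rounds to 548.
- CL201 ran 24 + 54 weeks (Protocol 5): 78 × 7 = 546 days.
- A 548-day window from UX007 initiation therefore holds 546 days of CL201 and 548 − 546 = 2 days of CL202.

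Early terminators are treated differently. Their events count from UX007 initiation to the termination visit, which mixes CL201 and CL202 time.

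**2. Post/pre ratio if all benefit is lost in CL202**

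Assumed rates per year: 1.5 pre, 0.75 in CL201, 1.5 in CL202. T is years of CL202 follow-up.

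| Reading of the post period | Calculation | Post/pre |
|---|---|---|
| 18 months from UX007 initiation | (546 × 0.75 + 2 × 1.5)/548/1.5 | 0.50 |
| Study period 2, T = 3 | (0.75 × 1.5 + 1.5 × 3)/4.5/1.5 | 0.83 |
| Study period 2, T = 5 | (0.75 × 1.5 + 1.5 × 5)/6.5/1.5 | 0.88 |
| Study period 2, T = 7 | (0.75 × 1.5 + 1.5 × 7)/8.5/1.5 | 0.91 |
| CL202 only | 1.5/1.5 | 1.0 |

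The CL202:CL201 ratio in the same scenario is 1.5/0.75 = 2.0. With assumed CL201:pre ratios of 0.3 and 0.7 instead of 0.5, the first row becomes 0.303 and 0.701. It tracks the CL201 effect and barely registers CL202.

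**3. How often a pre/post benefit would be declared under that loss**

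Gamma-Poisson simulation, 4,000 runs per setting. Assumptions: 20 to 30 rollovers, pre rate 1 to 2 per year, CL201:pre ratio 0.5, between-subject variance 1, no extra within-subject variance, CL202 follow-up 1.5 to 5 years. The test is a two-sided paired t-test at 0.05, borrowed from the naïve-cohort plan because the rollover section names none.
- 548-day window: about 50 to 94% of runs.
- Study period 2 pooled: about 5 to 45%.
- CL202 only: about 2%.
- A paired CL202-minus-CL201 contrast detected the loss in about 50 to 94% of runs with 1.5 CL202 years, and about 74 to 99% with 5.

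**4. Precision of the missing estimate**

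Assumptions: a constant on-drug rate of 0.5 to 1 per year, between-subject variance 1, extra within-subject variance 0.5, CL202 follow-up 2 to 4 years, 20,000 runs. The 95% interval extends either side of the CL202:CL201 ratio by this factor:
- 15 rollovers: 2.4 to 3.2
- 20 rollovers: 2.1 to 2.7
- 30 rollovers: 1.9 to 2.2

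For an observed doubling, the lower limit is 2/3.2 = 0.63 to 2/2.4 = 0.83 with 15 rollovers, and 2/2.2 = 0.91 to 2/1.9 = 1.05 with 30. This is less optimistic than step 3 because it allows the subject's rate to vary between periods.

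**The case against.** The strongest reply is that the plan already shows what is needed. CL201 and CL202 rates stand side by side, CL202 is split by 18-month interval, and patient-level plots and the individual profile figures in SAP 8.4.1 show events within subject. The primary analysis in SAP 8.5.1 uses CL202 time only and is presented by cohort. All of this stands. A reader might infer that nothing sets CL202 beside CL201, or that a complete loss would be reported as a benefit. The documents do not support either inference: in the scenario above the tables would show 1.5, 0.75 and 1.5.

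A reader might also infer that every version of the pre/post ratio falls below 1. It does not. SAP 8.5.5.2.1 offsets by time in the study, the parallel naïve-cohort text (8.5.4.2.1) equates that with study period 1, and 8.5.5.1 mentions follow-up on CL202. If post means CL202 only, complete loss gives 1.0. That reading conflicts with the study period 3 anchor and with Table 11.1.1, and it still yields no CL202:CL201 estimate.

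Next, maintenance is stated in the rationale rather than among the objectives, is not defined as CL202 against CL201, and concerns a diverse population, while the stated comparator is pre-treatment history. That limits the reach of the point. Naïve subjects have no CL201 period, and no pre-UX007 comparison is planned for the Other cohort, so the point covers rollovers only.

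Finally, the added estimate would be imprecise, and one pooled CL202 level could hide late waning. Both are fair, and the fix allows for them.

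**Conclusion.** The point holds for CL201 rollovers. Maintenance is assessed only descriptively there, and the one modelled contrast does not address it. On the SAP's own anchors the post window is 546/548 = 99.6% CL201 time for subjects with more than 18 months on CL202, so the post/pre ratio is nearly insensitive to later waning. Under complete loss it stays at about 0.50, or at 0.83 to 0.91 if study period 2 is pooled over 3 to 7 CL202 years. The 546 and 548 days follow from the documents. The ratios rest on assumed rates, and the simulation results also on assumed rollover numbers, dispersion and follow-up.

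No primary result is invalidated, and a complete loss would be visible in the planned CL202 summaries. What is missing is a within-subject estimate of the change from CL201 to CL202 with its uncertainty, together with a single definition of the post period. Both should be settled before the final analysis.

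**What to change.** In SAP 8.5.5.2.1:
- Replace the pre/post indicator with a period factor: study period 3, the CL201 treatment period, and CL202. Fit it once with CL202 as a single level and once with CL202 split into the 18-month intervals already planned, so that late waning is not averaged away.
- Use one row per subject-period with log(days in that period/365.25) as offset, and keep the same REPEATED subject structure.
- Report the CL202:CL201 and CL202:pre rate ratios with 95% confidence intervals, as estimates.
- State that a wide interval including 1 is not evidence of maintenance, and that selective retention of subjects who did well in CL201 can bias the ratio toward apparent waning.

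Then use one definition of the rollover post period in 8.5.5.1, 8.5.5.2.1 and Table 11.1.1, and add the model to the rollover MCE row of that table.

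The cost is a short SAP edit and a few extra contrasts from a model already planned, on CL201 and CL202 data already being integrated. It needs no new data or visits. The price is wide intervals, wider still for the later 18-month intervals if fewer subjects contribute to them.
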